A Randomized Trial of Betadine Bladder Irrigations vs. Standard of Care Prior to Indwelling Catheter Removal to Reduce Bacteriuria and Catheter-Associated Urinary Tract Infections

Principal Investigator

[name] MD

Co-Investigators

[name] MD [name] MD [name] MD [name] MD [name] RN

PROTOCOL DATE: SEPTEMBER 26, 2018

TABLE OF CONTENTS

I.	BACKGROUND AND RATIONALE	2
II.	Objectives and Endpoint	3
III.	Methodology	3
IV.	Risks and Benefits	6
V.	ELIGIBILITY CRITERIA	7
VI.	DATA ANALYSIS	8
VII.	DATA SAFETY MONITORING PLAN	10
VIII.	References	11
APP	ENDIX A: QUESTIONNAIRE	12

I. BACKGROUND AND RATIONALE

Indwelling urinary catheters are routinely used in the care of hospitalized patients for a variety of reasons, including monitoring of urine output in critically ill patients, relief of urinary obstruction, and prevention of contamination of decubitus ulcers. Bacteriuria increases by 3-10% each day a catheter is left in place^{1, 2} meaning that by 30 days, generally 100% of patients with indwelling catheters will have bacteria in their urine. The majority of these people do not have urinary tract infections (UTIs), they are merely colonized and do not require treatment.

Over the last decade, there has been great emphasis on reducing the incidence of hospitalacquired infections, including catheter-associated UTI (CAUTI). Hospitals have had relatively good results, though there is certainly still room for improvement. To define a standard (and ultimately to compare hospitals against each other), a surveillance definition for CAUTI³ has been developed by the National Healthcare Safety Network (NHSN). While useful for surveillance, the definition does not correlate with clinical UTIs, leading to over diagnosis and over-reporting of UTIs (in other words, those with merely bladder colonization being diagnosed as having a UTI). Despite continuing progress in standard methods of reducing infection rates (including decreasing the number of catheters inserted, ensuring proper catheter maintenance, and removing catheters when no long necessary) we continue to have unacceptably high rates of CAUTIs. As hospital-acquired infection rates are increasingly tied to reimbursement from governmental agencies, there is a great need to reduce infection, either by meeting surveillance criteria or through novel clinical approaches.

Studies from the 1980s and 1990s investigated a variety of compounds for local instillations into the bladder in attempts to decrease bacteriuria and prevent infections. One of the more promising solutions instilled was povidone-iodine. A single preoperative instillation of 1% povidone-iodine prior to prostatectomy in patients with indwelling catheters reduced the rate of post-operative bacteriuria from 100% to 22.5%⁴. Similarly, bladder irrigation with 2% povidone-iodine prior to prostatectomy in patients with indwelling catheters was well tolerated and achieved urine sterilization in 75% of patients in another study⁵. While neither of these studies looked at reducing rates of CAUTI, we hypothesize that they could provide a benefit, given their effectiveness at decreasing bacteriuria in patients with indwelling catheters. Both studies

reported that a low concentration of 1 or 2% was well tolerated by patients. A study from the Netherlands evaluated use of pre-removal povidone-iodine bladder irrigation⁶. No reduction in bacteriuria was found in cultures at days 4 to 14 after removal, though there was a trend towards less bacteriuria in the first 3 days after removal. Additionally, more than half of the patients had only had catheters in place for 3 days or less prior to removal, and only 13.6% of patients had positive urine cultures prior to removal, which may have minimized the potential differences.

A single dose of povidone-iodine prior to catheter removal seems a novel and promising practice for several reasons. First, we suspect it will be helpful in reducing rates of NHSN defined CAUTI, as these are still diagnosed for 2 days after the catheter is removed. Results of a recent review revealed that 15-20% of diagnosed CAUTIs at Beaumont occurred during this window. Second, using multiple doses of povidone-iodine would be inadvisable, since we suspect bacteria over time would become resistant even to this antiseptic. Third, we suspect use of an antiseptic is preferable to an antibacterial for preventing further antimicrobial resistance development. Finally, use of this method, as opposed to the suggested use of systemic antibiotics at time of removal⁷, is potentially preferable from the downstream standpoint of less antimicrobial resistance and reduced risk of *Clostridium difficile* infection.

II. OBJECTIVE AND ENDPOINT

Objective:

To evaluate the effectiveness of Betadine irrigation solution (2% povidone-iodine) instilled into the bladder immediately prior to indwelling catheter removal to decrease the risk of subsequent bacteriuria, leading to decreased rates of NHSN defined CAUTI.

Endpoint:

Presence or absence of NHSN defined CAUTI at 48-72 hours after indwelling urinary catheter removal, as assessed by urinalysis (UA), urine culture (UC), and UTI Symptom Assessment questionnaire (UTISA)⁸.

III. METHODOLOGY

A total of 110 men will be enrolled in this randomized trial, which will be conducted at Beaumont Hospital, Royal Oak. Eligible patients will be consented and randomized into 1 of 2

groups. Ideally, fifty-five men will be in each group. 120 men may need to be enrolled to achieve the desired number of patients completing the 48-72-hour post-catheter removal visit, which is the study endpoint.

Despite optimal "clean catch" collection techniques, it is often difficult to obtain a noncontaminated urine sample from females without performing sterile catheterization due to the chronically colonized vaginal flora. In order to minimize patient risks and difficulty with recruitment associated with additional catheterization, we have chosen to exclude females from this initial study. The male anatomy allows for adequate sample collection via "clean-catch" alone. By enrolling only males we hope to reduce the possibility of contamination in the cleancatch specimens collected at the 48-72 hour follow up visit⁹. Future studies would include females as well.

Study staff will review patient charts from all Beaumont Hospital, Royal Oak units (including rehabilitation units) in order to identify patients who may be eligible to participate. Appropriate patients will be approached, the study will be described to them in detail, and informed consent will be obtained. Eligibility criteria will be reviewed, including current antibiotic use, which is exclusionary. If the patient meets all of the inclusion criteria and none of the exclusion criteria, a urine sample will be obtained for UA and UC. All urine test results will be for research purposes only and not part of the patient's clinical chart/electronic medical record. All UA and UC results, collected for research, will be reviewed by one of the study investigators. If a patient develops symptoms at any point in the study, a UA and UC could be obtained at the care provider's discretion.

Patients will be randomized 1:1 to receive either standard of care (catheter removal with no bladder irrigation) or bladder irrigation with 2% povidone-iodine solution immediately prior to catheter removal. Randomization envelopes will be provided by the biostatistician and stored in a secure location in Urology Research. At the time research staff contact the pharmacist with the Betadine request, group assignment will be verified.

The first group will receive standard of care (SOC) only (indwelling catheter removal without any other interventions). If the patient is randomized to the SOC arm, the research nurse will simply remove the indwelling catheter. The second group will receive a single dose of approximately 60 cc of 2% povidone-iodine (Betadine) placed into the bladder. When the patient is randomized to the Betadine rinse arm, the research pharmacist will be contacted. The pharmacist will prepare and deliver the Betadine filled syringe to the research staff for instillation. The Betadine solution will be instilled through the catheter and left to dwell for 10 minutes, drained, and then the catheter will be removed. Research staff will be trained by a physician to remove the catheter using aseptic technique and prevent introduction of bacteria. To ensure patients are able to adequately void after catheter removal, designated study personnel (Urologists), will manage the study patient's voiding trial.

48-72 hours after catheter removal a urine sample will be obtained to repeat UA and UC. If enrolled patients are still inpatient at this time point, study staff will see the patient in the hospital and conduct the Visit 2 activities. If the patient has been discharged from the hospital, this visit will occur in the Urology Research office. While not ideal or preferred, if the patient is not available for an in-person visit, the questionnaire may be completed over the phone, or sent to the patient and returned by mail (returned by USPS, email, or fax). In addition to the UA and UC, the UTISA questionnaire will also be completed. The UTISA questionnaire is a validated tool which will be utilized to assess the "severity" and "bothersomeness" of the most frequently reported signs and symptoms of uncomplicated UTI⁸. The Beaumont laboratory will evaluate all collected specimens. If a patient develops symptoms suggestive of a UTI, then further testing may be performed at the discretion of their managing physician or one of the study investigators. Research staff will also contact patients by phone at 7 and 28 days after catheter removal. At that time the UTISA will be administered to assess urinary symptoms, including diagnosed UTIs since the time of catheter removal. The UTISA may be completed verbally over the phone or by mail (returned by USPS, mail, or fax). If the patient's responses indicate a possible UTI, the patient will be referred to their primary care provider and/or other health care provider for evaluation.

Patients requiring reinsertion of an indwelling catheter prior to study completion will be withdrawn from the study. Patients that do not comply with the study protocol may also be withdrawn from the study by the Principal Investigator (PI).

	Screening & Treatment Visit Inpatient Visit	Visit 2 48-72 Hours Clinic or Inpatient Visit	Visit 3 7 ± 3 days Phone Call	Visit 4 28 ± 3 days Phone Call
Informed Consent	Х			
Review Inclusion and Exclusion Criteria	Х			
Review of Current Antibiotic Medication Use	Х	Х	X	Х
Urine collection: UA & UC	Х	Х		
UTISA Questionnaire		Xa	Xb	Xb
Indwelling Catheter Removal	Х			
Betadine Bladder Irrigation	Xc			
Assess for Adverse Events	Х	Х	X	Х

SCHEDULE OF ACTIVITIES

^aAt Visit 2 the UTISA may be completed in person, over the phone, or by mail (returned via USPS, email, or fax). ^bAt visits 3 and 4 the UTISA may be completed over the phone or by mail (returned via USPS, email, or fax). ^cBetadine Bladder Irrigation will only be completed with those patients who are randomized to the treatment group.

IV. RISKS AND BENEFITS

Potential Benefits: This intervention may be beneficial for both patients and the hospital. The rate of hospital acquired CAUTIs may be reduced without increasing the risk of antimicrobial resistance.

Potential Risks:

Risks of Urinary Catheterization:

Less Frequent (occurring from 1% to 10% of the time):

- Temporary inability to urinate
- Bleeding
- Mild cramping
- Urinary tract infection

Risks of Betadine:

Less Frequent (occurring from 1% to 10% of the time):

• Local irritation of the bladder

Rare (occurring less than 1% of the time):

• Allergic reaction

Unknown Risk:

• Brown discoloration of urine

Risks of Bladder Irrigation:

Less Frequent (occurring from 1% to 10% of the time):

• Discomfort while the indwelling urinary catheter is clamped

All patients will be closely monitored by the research staff during the instillation, if applicable, and during catheter removal. All unanticipated problems will be reported to Beaumont's Investigational Review Board (IRB) per policy.

V. COMPENSATION

Patients will be reimbursed for time and travel during the course of the study, as outlined in the table below. Stipend checks will be sent, via US mail, in the amount listed below after each completed visit which is eligible to receive a stipend. If patients are unable to complete all study visits, they will be paid only for the visits they were able to complete.

Visit	Stipend Per Visit
Screening and Treatment Visit	\$25.00
Study Visit 2	\$25.00
Study Visit 3	\$0.00
Study Visit 4	\$0.00
Maximum Total (if all visits are included)	\$50.00

VI. ELIGIBILITY CRITERIA

Inclusion:

- 1) Provide written informed consent and the willingness and ability to comply with all aspects of study requirements
- 2) Male
- Inpatients ≥ 18 years of age with an indwelling catheter in place for at least 5 days with a plan for removal

Exclusion:

- 1) Patients planned for discharge with an indwelling catheter in place
- 2) Patients unable to report urinary symptoms accurately
- 3) Patients with hyper-sensitivity or allergic reaction to Betadine, iodine, shellfish or other related compounds
- 4) Clinical signs or symptoms of urinary tract infection at the time of consent
- 5) Patients currently being treated for UTI
- 6) Patients currently taking any antibiotic medication, other than those listed in Appendix B
- 7) Patients already taking medications known to potentially irritate the bladder, such as, but not limited to, cyclophosphamide, ifosfamide, and other chemotherapeutic agents
- 8) Patients with history of bladder cancer, pelvic radiation or interstitial cystitis
- 9) Patients unable to comply with study requirements
- Any other condition which, per investigators' judgment, may increase patient risk and/or impede the reliability of study data

VII. DATA ANALYSIS

An infection rate of 25% is anticipated at day 2 post catheter removal for the SOC group. A difference has been shown of a 75% drop in infection rate using povidone-iodine bladder irrigation⁵. A power analysis using these estimates yields 55 patients needed in each arm to have 80% power at a 0.05 significance level to detect a difference of 25% versus 6.25%. We estimate at most a 10% dropout rate and plan to enroll 60 patients per arm to account for this.

Descriptive statistics will be provided for all data collected. Categorical variables will be reported as counts and percent frequencies. All continuous variables will be reported as means

+/- the standard deviation followed by the median, minimum to maximum or the median (25th, 75th percentiles) then minimum to maximum dependent on the normality of the data.

The endpoint of presence or absence of bacteriuria at 48-72 hours post catheter removal will be examined with a Fisher's exact tests, odds ratio and 95% confidence intervals. If any differences are found in what appear to be confounders for UA, a multivariate logistic regression analysis may be completed adjusting for these differences.

The categorical variables will be examined using Pearson's Chi-square tests where appropriate (expected frequency >5), otherwise Fisher's exact tests will be used. Continuous variables will be examined for normality. Normally distributed variables will be analyzed using t-tests. Non-normally distributed variables will be examined using non-parametric Kruskal-Wallis tests.

REDCap (Research Electronic Data Capture) is the web-based software program that will be utilized for data collection and management. Urology Research will be responsible for all data management responsibilities including, but not limited to, database creation, data entry and query resolution. Data analyses will be performed by a Beaumont Biostatistician utilizing statistical software.

VIII. DATA SAFETY MONITORING PLAN

Ongoing safety monitoring will be performed by the study staff, including the PI and coinvestigators. The PI will have ultimate responsibility of assuring patient safety. A Medical Safety Monitor (MSM) will be assigned by the PI. The MSM will be a physician who is not involved in the study and who has no conflict of interest. The MSM will review Serious Adverse Events (SAEs) and will determine expectedness and causality of the event. The MSM may suggest protocol modifications to prevent the occurrence of adverse events (e.g., modifying the protocol to require frequent measurement of laboratory values predictive of the event or to improve expeditious identification of SAEs). If the MSM is unavailable for an extended period (i.e. extended vacation, illness, etc.) a back-up MSM will be nominated by the study PI. Safety issues will also be addressed in the annual reports to Beaumont's IRB. Additional data safety monitoring procedures include:

- Research Administration's Clinical Research Quality and Process Improvement Program (CRQIP) will perform in-house monitoring of the first patient enrolled after the completion of visit 1
- Safety data review at study team meetings

IX. REFERENCES

- Warren, J. W., Platt, R.J., Rosner, B., & Kass, E. H. (1978). Antibiotic irrigation and catheterassociated urinary-tract infections. *New England Journal of Medicine*, 299, 570-573. doi:10.1056/NEJM197809142991103

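### The endpoint is labelled NHSN CAUTI, but its 48-72 hour urine sample falls wholly or partly after the 2-day window in which the protocol says NHSN CAUTI is diagnosed

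*Combined protocol and SAP*

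**What the plan says.** - **Section I (Background and Rationale).** The first argument for a single dose before removal is an expected fall in NHSN CAUTIs, "as these are still diagnosed for 2 days after the catheter is removed". A review at the hospital is cited: "15-20% of diagnosed CAUTIs at Beaumont occurred during this window".
- **Section II (Objective and Endpoint).** The endpoint is "Presence or absence of NHSN defined CAUTI at 48-72 hours after indwelling urinary catheter removal", judged from urinalysis, urine culture and the UTISA questionnaire. The objective puts less bacteriuria first and lower NHSN CAUTI rates as its consequence.
- **Section III (Methodology).** "48-72 hours after catheter removal a urine sample will be obtained to repeat UA and UC". The Schedule of Activities shows urine collection only at the treatment visit and at Visit 2. Before Visit 2, testing depends on symptoms: "If a patient develops symptoms at any point in the study, a UA and UC could be obtained at the care provider's discretion". The calls at 7 and 28 days are meant to cover symptoms and any UTI diagnosed since removal.
- **Section VII (Data Analysis).** "An infection rate of 25% is anticipated at day 2 post catheter removal for the SOC group". The outcome then tested is bacteriuria at 48-72 hours.

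The plan does not say how the 2 days are counted, does not reproduce the NHSN criteria (it cites the manual), and does not say how a first positive after the window, or a UTI diagnosed before Visit 2, is classified.

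**The concern.** The trial is justified by infections attributed to the catheter in the 2 days after removal. Scheduled measurement opens as that period closes: no urine and no questionnaire is planned between removal and hour 48. An infection that appears and is treated on the first day may leave no trace in the Visit 2 sample. An infection first found at hour 65 may be too late to be an NHSN CAUTI. With the endpoint labelled as it is, either a difference or a null result at 48-72 hours would invite a conclusion about NHSN CAUTI that the measurement may not support.

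This concerns the time of measurement. It would remain if Section VII were changed to analyse CAUTI instead of bacteriuria.

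**Working it through.** **The plan's own figure.** Section VII gives 55 per arm for 25% versus 6.25%, 80% power and a 0.05 level. With unpooled variance and a two-sided test:

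n = (1.960 + 0.842)² × (0.25 × 0.75 + 0.0625 × 0.9375) / 0.1875² = 7.849 × 0.2461 / 0.03516 = 54.94, so 55.

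The figure reproduces and does not depend on the present point.

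**Overlap of the visit with the window.** Inputs: a window of 2 days after removal (Section I) and a visit from 48 to 72 hours (Sections II and III), so 24 visit hours. The counting rule is not given, so each reading below is an assumption. Let h be the clock hour of removal and E the end of the window in hours after removal. Overlap = max(0, min(72, E) − 48).

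| Reading of 2 days | E | Overlap with the visit |
|---|---|---|
| Elapsed time | 48 | 0 of 24 h (they touch at hour 48) |
| Calendar days, removal day = day 1 | 48 − h | 0 of 24 h for any h |
| Calendar days, removal day = day 0 | 72 − h | 24 − h hours, a share of (24 − h)/24 |

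On the third reading:

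- removal at 08:00: 16 h, 16/24 = 67%
- removal at 12:00: 12 h, 12/24 = 50%
- removal at 16:00: 8 h, 8/24 = 33%

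On that same reading, a sample at hour 60 is inside only if 72 − h ≥ 60, that is, removal by 12:00. A sample at hour 70 is inside only for removal by 02:00. Two men with the same results at the same elapsed time could therefore differ in NHSN status because of the clock time of removal.

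**What else reaches into the window.** The UTISA (Appendix A) asks about the past 24 hours. Completed at hour t, it covers t − 24 to t, so the part before hour 48 is 72 − t hours: 24 h at t = 48, 12 h at t = 60 and none at t = 72. It records symptoms, not urine, and never reaches the first 24 hours. Discretionary testing and the later calls can find earlier events, but only in men with symptoms or through recall.

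**What cannot be computed.** The documents give no NHSN CAUTI rate inside or after the window. The 15-20% is a share of all diagnosed CAUTIs, not a risk per patient. Neither the bias nor the expected number of in-window events can be derived.

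**The case against.** The strongest reply is that the counting rule sits in a manual the plan only cites. If 24-hour blocks from removal are numbered from 0, the block from 48 to 72 hours is day 2 and the overlap is complete. Section VII could be using that convention, since it puts the control rate at day 2 and tests the outcome at 48-72 hours. This explains the day 2 wording in Section VII, which may simply mean Visit 2 and need not be a further time point. It fits Section I poorly: there, 2 days is a duration, and hours 48 to 72 are the third day of elapsed time.

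The timing also has a rationale. Section I reports that an earlier randomized study saw a trend towards less bacteriuria in the first 3 days after removal and no reduction at days 4 to 14. A 48-72 hour sample lies within those 3 days, and a bacteriuria comparison needs no attribution window. That stands, and it is the reason to keep the visit. It supports a bacteriuria endpoint, not the NHSN label.

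Two stronger inferences are tempting. A reader might infer that Visit 2 cannot measure NHSN CAUTI at all. The documents do not support this: partial overlap is possible on the day-0 count, symptomatic men may be tested earlier, and the UTISA looks back 24 hours. A reader might also infer that a man first positive at hour 60 or 70 will be scored as an NHSN CAUTI. No rule says so, and the NHSN label could equally mean that the attribution limit is applied. The documented fault is that the classification is left open.

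**Conclusion.** The point holds as a mismatch between the endpoint's label and the time of its measurement. The visit lies wholly after the stated window on two of the three readings tabulated, and partly inside it on the third (67%, 50% or 33% for removal at 08:00, 12:00 or 16:00). Events within the window are captured only through discretionary testing and later recall, and a first positive late in the visit may fall outside the NHSN definition. The 48-72 hour comparison can answer a question about bacteriuria. It cannot be read straightforwardly as an effect on NHSN CAUTI.

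This rests on Section I's own statement of the 2-day window and on the assumed counting rules shown; no outside NHSN rule was used. The sample size is not affected. The matter goes beyond a missing detail, because it concerns the only endpoint named in Section II and changes what the trial can conclude.

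**What to change.** 1. Keep Visit 2 at 48-72 hours, name its endpoint bacteriuria, with or without symptoms, at 48-72 hours after removal, and drop the NHSN label from it in Section II.
2. Report NHSN CAUTI as a separate outcome that counts only events dated within 2 days of removal. State how the days are counted, and whether a Visit 2 research culture that falls inside the window counts. Use the clinical testing already allowed and the diagnosed-UTI information that Section III says is collected at days 7 and 28. The questionnaire printed in Appendix A has no item for a diagnosis or its date, so the case report form should record both.
3. Use one time point in Sections II, III and VII, including the power statement, in place of both day 2 and 48-72 hours.

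**Cost.** One amendment and a date field, with no extra visit, test or patient. The headline endpoint is no longer NHSN CAUTI, and few NHSN events may be counted, so that outcome is likely to be descriptive. Its ascertainment depends on discretionary testing, so the number of men tested before Visit 2 should be shown by arm.

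Moving Visit 2 earlier is an option for the sponsor to weigh, not a required change. It would bring the sample closer to the NHSN window but say less about how long any effect on bacteriuria lasts, and a single earlier sample would still not cover the whole window.

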Appendix A: Urinary Tract Infection Symptom Assessment (UTISA)

		I	About Yo	our Symptoms and Their Impact o	on Your Life	e		
Please indicate whether you have had the following symptoms/problems in the past 24 hours and how severe they were: (Please circle one number for each symptom) Did not have Mild Moderate Severe				SYMPTOMS	If you have experienced these symptoms/problems in the past 24 hours, please indicate how bothersome they were (Please circle one number for each symptom) Not at all A little Moderately A lo			nours, v were?
0	1	2	3	Frequency of urination (going to the toilet very often)	0	1	2	3
0	1	2	3	Urgency of urination (a strong and uncontrollable urge to pass urine)	0	1	2	3
0	1	2	3	Pain or burning when passing urine	0	1	2	3
0	1	2	3	Not being able to empty your bladder completely/passing only small amounts of urine	0	1	2	3
0	1	2	3	Pain or uncomfortable pressure in the lower abdomen/pelvic area caused by your urinary tract infection	0	1	2	3
0	1	2	3	Lower back pain caused by your urinary tract infection	0	1	2	3
0	1	2	3	Blood in your urine	0	1	2	3

8. Please give an overall rating of the severity of your urinary tract infection symptoms as they are at this moment *(Please circle the number of your answer)*

0 No symptoms 1 Mild 2 Moderate 3 Severe

Additional questions at Visits 3 and 4:

9. Since you last completed this questionnaire, have there been any changes in your urinary tract infection symptoms? (*Please circle the number of your answer*)

- 0 about the same
- 1 better (if patient responded 1=better, go to question 10)
- 2 worse

10. Please indicate how much better (Please circle the number of your answer)

- 6 a very great deal better
- 5 a great deal better
- 4 a good deal better
- 3 moderately better
- 2 somewhat better
- 1 a little better

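### The planned data (urinalysis, culture and UTISA) are not shown to yield the NHSN-defined CAUTI that Section II names as the endpoint

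*Combined protocol and SAP*

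**What the plan says.** - **Endpoint (Section II).** NHSN-defined CAUTI, present or absent, 48-72 hours after removal, "as assessed by urinalysis (UA), urine culture (UC), and UTI Symptom Assessment questionnaire (UTISA"). No culture threshold, UTISA cut-off or combining rule is given, and the NHSN criteria are not written out.
- **Objective (Section II).** Betadine is given "to decrease the risk of subsequent bacteriuria, leading to decreased rates of NHSN defined CAUTI". Bacteriuria is thus a step towards CAUTI, not the same thing.
- **View of the NHSN definition (Section I).** The protocol says that "the definition does not correlate with clinical UTIs, leading to over diagnosis and over-reporting of UTIs", which it explains as "those with merely bladder colonization being diagnosed as having a UTI". It adds that NHSN CAUTI can still be diagnosed for two days after removal, and that 15-20% of the hospital's diagnosed CAUTIs fell in that period.
- **Symptom instrument (Section III and Appendix A).** The UTISA rates the "most frequently reported signs and symptoms of uncomplicated UTI". Its seven items are frequency, urgency, pain or burning on voiding, incomplete emptying, lower abdominal or pelvic pain, low back pain and visible blood, each over the past 24 hours. An overall severity rating follows.
- **Schedule of activities (Section III).** Visit 2 has urinalysis, culture, UTISA, antibiotic review and adverse events. No temperature or vital signs are listed at any visit.
- **Analysis (Section VII).** The outcome to be compared by Fisher's exact test is bacteriuria at 48-72 hours, with no symptom requirement.

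**The concern.** The rationale is about a reportable event: Section I speaks of surveillance rates tied to reimbursement and of CAUTIs diagnosed in the two days after removal. The trial answers that question only if its data can classify each man by the surveillance definition. The one symptom source was made for another purpose, looks back one day and has no systemic item. The protocol itself says that the surveillance definition does not track clinical UTI, so a clinical symptom scale cannot be presumed to stand in for it. Section VII then analyses a different outcome. A result reported as NHSN CAUTI might therefore say little about whether the hospital's reportable rate would change.

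**Working it through.** **1. The plan's own figure.** Section VII gives 25% versus 6.25%, significance level 0.05, 80% power and 55 per arm. The unpooled two-sided normal approximation gives n = [p1(1-p1) + p2(1-p2)] × (1.960 + 0.842)² / (p1-p2)² = (0.1875 + 0.0586) × 7.849 / 0.1875² = 54.9, so 55. The figure reproduces; the problem is not arithmetic. The 25% is called an infection rate and the 75% drop comes from a study that Section I describes as measuring urine sterilization. Neither figure is tied to NHSN CAUTI.

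**2. What the UTISA recall covers.** Inputs: Visit 2 at t = 48 to 72 hours after removal (Section III); recall 24 hours (Appendix A); attribution period two days (Section I), read here as hours 0 to 48. The recall runs from t-24 to t, so its overlap with hours 0 to 48 is 48 - (t-24) = 72 - t hours.

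| UTISA completed at | Recall covers | Overlap with 0-48 h | Not covered |
|---|---|---|---|
| 48 h | 24-48 h | 24 h | 24 h |
| 60 h | 36-60 h | 12 h | 36 h |
| 72 h | 48-72 h | 0 h | 48 h |

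The first 24 hours are never covered, because t-24 is at least 24. If the manual counts calendar days, the period could end later, but a 24-hour recall still covers at most 24 hours of it and still misses the first day.

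**3. What the UTISA items cover.** All seven are urinary, pelvic, low-back or visible-blood items; none is systemic. Two also presuppose a diagnosis, for example "Lower back pain caused by your urinary tract infection". Yet Section VI excludes men with signs or symptoms of UTI at consent, and Section III keeps the research urine results out of the clinical chart, so many men would have no diagnosis to attribute pain to.

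**4. The two possible readings of the endpoint.**
- *UTISA symptoms required, with a positive culture.* Any case that qualifies through a sign outside the UTISA, or through a symptom that resolved before the recall began, is missed.
- *UTISA symptoms not required.* The endpoint is bacteriuria, as in Section VII. The protocol separates this from CAUTI: the objective has one leading to the other, and Section I says that most catheterised patients with bacteriuria are only colonised and that the two prostatectomy studies of bacteriuria did not look at CAUTI.

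Neither reading is shown to give the event named in Section II.

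**5. Why the choice matters for power (illustration only).** The documents give no rate under either reading. Keeping the 75% relative reduction and 55 per arm, pooled two-sided power is 78% at an assumed standard-of-care rate of 25%, 67% at 20% and 37% at 10%. Exact power for the planned Fisher's test is 72%, 57% and 19%. These show sensitivity to the rate and do not estimate it.

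**The case against.** The best defence is that Section II keeps the NHSN definition and merely lists tools; it does not say that the UTISA replaces the definition's criteria. Adverse events are assessed at Visit 2, care providers may order tests if symptoms arise, and the day 7 and day 28 calls are meant to pick up diagnosed UTIs. Systemic illness would not go wholly unseen. This is fair, but none of these is named as an endpoint component, none is a specified measurement of the NHSN criteria, and the later calls fall after the endpoint.

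Several stronger inferences are tempting, and the documents do not support them:
- *That all three components capture only local symptoms.* Urinalysis and culture are laboratory tests, and culture can detect colonisation. Only the UTISA is a symptom measure.
- *That colonised, symptom-free men would be counted as not having the endpoint.* No text requires a positive UTISA. Under Section VII a man with a positive culture counts as having bacteriuria whatever his symptoms. Nor need a colonised man score zero: Section IV lists bleeding, cramping, temporary inability to urinate and bladder irritation as risks of the procedures, and several UTISA items could register these.
- *That fever is the missing criterion, or that a given share of events is lost.* The manual is cited, not reproduced. Section I says that the definition over-diagnoses, but not through which criterion. Any percentage would be a guess.

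**Conclusion.** The concern holds in a limited form. The endpoint carries the NHSN label, but the plan neither writes out a rule for applying that definition nor schedules data shown to be sufficient for it, and Section VII analyses something else. The measurable part is the recall gap: at least 24 of the 48 hours after removal are outside the UTISA, rising to all 48 for a visit at 72 hours. This rests on reading two days as 48 hours and on completion of the form within the visit window. The number of events misclassified, and the direction of any effect on the treatment comparison, cannot be stated from the documents. The consequence is for interpretation: as planned, the trial can report on bacteriuria, or on bacteriuria with UTISA symptoms, but cannot claim a change in the NHSN surveillance rate.

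**What to change.** **Preferred.** In Section II, apply the criteria of the cited NHSN chapter and write out the rule that turns them into presence or absence. Add to the schedule every item those criteria require, including temperature if the chapter lists it, covering removal through the end of the attribution period. Take these from routine vital signs for inpatients, and ask about the whole period at Visit 2 for discharged men. Use the UTISA only for the symptoms that the chapter lists. Make Section VII analyse this same endpoint, and say which endpoint the 25% versus 6.25% refers to.

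**Otherwise.** If those data will not be collected, drop the NHSN label and use one name in Sections II and VII for what is analysed: bacteriuria, or bacteriuria with UTISA symptoms at a stated cut-off.

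**Cost.** The first option needs one or two case report form fields and one question at Visit 2. Its drawback is that systemic signs in inpatients can have other causes, so they add events unrelated to the bladder. The second option needs only edited text, but gives up the claim about reportable CAUTI.
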